 6. Good general and oral health

- Exclusion Criteria:** for the involved subjects included:
 1. Patients suffering from any systemic diseases interfering with tooth movement.
 2. Patients with extracted or missing permanent teeth. (except for third molars).
 3. Patients with badly decayed teeth.
 4. Patients with any parafunctional habits (i.e. Bruxism, tongue thrusting, mouth breathing, etc...).
 5. Patients with previous orthodontic treatment

C] Interventions:

➤ **Medical History Questionnaire:**

For every patient, to exclude the presence of any systemic condition interfering with orthodontic treatment.

➤ **Clinical Examination:**

Oral structures will be examined to identify caries, fracture or missing teeth. Gingival tissues will be carefully examined for any gingivitis, periodontitis, recession, or lesions.

➤ **Diagnosis**

Check the potential patient to fulfill the previously mentioned inclusion criteria. Every participant will be asked to sign an informed consent about the study. Full set of records (study models, panorama radiograph and lateral cephalometric radiographs, photos) will be taken for every patient as part of the routine procedure for treatment of patients in the clinic of the Orthodontic Department, Future University.

➤ **Clinical Procedure:**

After taking pre-treatment records, every patient will receive:

- Bonding of all teeth except for first premolars and banding/bonding the first and second molars will be done using Roth prescription brackets (0.022 x 0.028 slot)*.
- Miniscrews** will then be placed in the upper arch between the second premolar and first molar.

*American Orthodontics

** Jeil Miniscrews

- The patient will be referred for extraction of first premolars.
- Anchorage will be secured, followed by Leveling and alignment for the bonded and banded teeth through following the wire sequence: 0.014 NiTi, 0.016×0.022 NiTi and 0.017×0.025 StSt.
- After levelling and aligning is completed (right before retraction), the patient will be referred for the uptake of pre-intervention records.

➤ **Acquisition of pre-intervention records:**

- The patient will be referred for the uptake of a Lateral Cephalometric radiograph, which will be considered the T0 record.
- Impressions will be taken before retraction (without the archwire in place) followed by digital scanning of produced models.

➤ **Begin of Retraction:**

Frictionless group:

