- A ligature wire extended between the second premolars and miniscrews will be used for proper anchorage control.
- Closing retraction T-loops will be fabricated using 0.017 x 0.025 TMA wire. The loop will be positioned halfway the extraction space and the canine.^{35,36}.
- A gable angle of 45° will be added.
- Distal activation of 4 mm will be done with cinch back the wire distal to 2nd molars bilaterally.³⁷

Friction group:

- Crimpable hooks added to the arch wire (0.017"x0.025" Stainless steel) distal to the lateral incisor passing near the center of resistance of the anterior segment.
- Retraction will start on a 0.017"x0.025" Stainless steel wire using elastomeric chain (force applied will be 212 g per side)³⁸ extending between the crimpable hooks and the miniscrew.
- The force will be measured by a force gauge and reactivated every 4 weeks maintaining constant force of retraction all over the retraction phase.

➤ **Follow up visits**

Patients will be asked to attend for follow up sessions every 4 weeks for:

- Evaluation miniscrews stability.
- Replacement of the power chain to maintain a force of 212 gm per side.
- Reactivation of the T-loop by further distal activation and cinch back.
- Impression taking to determine the overall rate of retraction.

➤ **Criteria for discontinuing or modifying the allocated intervention:**

In cases of prolonged swelling or pain related to the miniscrew, the patient will be given strict oral hygiene measures and may wait for three weeks before the beginning of retraction.

In cases of loose or broken miniscrews, the screw will be removed and replace the miniscrew after complete resolution of the inflammation.

□ **Post-retraction Questionnaire:**

The patients of both groups will be asked to fill in questionnaires regarding their experience with their allocated technique

□ **Retraction records**

Following en-masse, patients will be referred to the same radiology center to acquire the final lateral cephalometric x-ray to assess the movement and inclination of anterior teeth.

The final dental model will assess the rate of retraction, molar rotation, and molar anchorage loss achieved throughout the study.

□ **Material Used**

- American Orthodontics Brackets, Roth prescription, 22 slot size.
- American Orthodontics Elastomeric power chains
- American Orthodontics Elastomeric O-ties
- American Orthodontics Ligature wire.

- Jiel Miniscrew, 8 mm TAD
- American Orthodontics Arch wires.

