- American Orthodontics Molar bands/tubes.

D] Outcomes

[figure not shown]
Primary outcome: is to monitor the rate of space closure during en-masse retraction. All outcomes will be assessed as the difference between T0 at the start of retraction and T1 after complete space closure.

Secondary outcomes: is to monitor the changes in the anterior teeth position (torque and vertical position), molar rotation, anchorage loss, and pain associated with the different methods used for retraction.

E] Participant timeline:

1. The principle investigator will screen the potential patients through careful clinical examination of patients at the orthodontic department, Faculty of Oral and Dental Medicine, Future University.
2. All recruited patients should fulfil the previously mentioned inclusion and exclusion criteria.
3. Every participant will be asked to sign an informed consent before the beginning of the study.
4. After patient's enrolment, each participant will be asked for pre-intervention records to ensure proper diagnosis.

5. The principle investigator will randomly allocate the patients to one of the intervention groups.
6. Anchorage will be secured by placement of miniscrew, followed by extraction of the first premolar.
7. Active intervention will begin after proper levelling and alignment of the upper arch.
8. The principle investigator will take pre-retraction records for every participant T0.
9. In Friction mechanics group, Power chain is used for anterior segment retraction while in Frictionless group, T-loop is used for retraction.
10. Each patient will come every 4 weeks for follow up visit, for appliance activation and uptake of impression for interim records.
11. After complete space closure, the principle investigator will take post-retraction records for each participant T1.
12. Every patient will fill up a questionnaire regarding his experience during treatment.
13. The principle investigator will continue the normal treatment and achieve proper finishing for every patient after the end of the study.

E] Sample size calculation:

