Our sample size calculation is based on a previous study comparing the effect of friction and frictionless mechanics²⁴. Using PS software output, we are planning a study of a continuous response variable from independent Group I and Group II subjects with 1 Group I(s) per Group II subject. In a previous study the response within each subject group was normally distributed with standard deviation 0.76. If the true difference in the Group II and Group I means is 1.0, we will need to study 10 Group II subjects and 10 Group I subjects to be able to reject the null hypothesis that the population means of the Group II and Group I are equal with probability (power) 0.8. The Type I error probability associated with this test of this null hypothesis is 0.05. Considering drop out a sample size 15 per group is appropriate.

F] Recruitment strategy:

The principal investigator will recruit the patients from the clinic of Orthodontic department, Faculty of Oral and Dental Medicine - Future University.

Screening of patients will continue until the total number of participants for the study is collected.

II) Assignment of interventions:

A] Sequence generation:

The supervisor of the study will apply Computer generated random numbers to randomly assign patients to group A (Frictionless) or B (friction) using Microsoft Office Excel 2007 sheet. The patient numbers will be written in the first column, and the supervisor will select function RAND() to generate the randomization number in the second column. These numbers will be sorted according to the randomization number so the first column numbers will be randomly distributed.

B] Allocation concealment mechanism:

The supervisor of the study will write the randomization numbers of the patients on opaque white papers folded three times to form sealed envelopes and store it inside a box. The codes for randomization will be securely held at the secretary's office.

C] Implementation:

At the time of intervention, the main operator will send the patient to the secretary's office. Then, the assigned employee will open the box and ask the patient to select one envelope. The main operator will assign each participant for the corresponding intervention either (friction or frictionless group) according to the list of codes of randomization.

Assignment to either intervention will occur before levelling and alignment stage.

D] Blinding:

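### Patients are allocated before miniscrews, extraction and levelling, which are the same in both arms; allocating just after T0 would remove an avoidable risk of bias

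*Combined protocol and SAP*

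**What the plan says.** The Implementation section fixes the time of allocation: "Assignment to either intervention will occur before levelling and alignment stage". The participant timeline gives the same order. Item 5 reads "The principle investigator will randomly allocate the patients to one of the intervention groups", item 6 is miniscrew placement and extraction, item 7 has active intervention begin after levelling, and item 8 reads "The principle investigator will take pre-retraction records for every participant T0".

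The Clinical Procedure part of the Interventions section describes the preparation once, for both arms. It opens with "After taking pre-treatment records, every patient will receive" and covers bonding, miniscrews, extraction and "Leveling and alignment for the bonded and banded teeth through following the wire sequence: 0.014 NiTi" and the later wires. T0 comes at the end of that phase: "After levelling and aligning is completed (right before retraction), the patient will be referred for the uptake of pre-intervention records". The first step that depends on the arm comes under the heading on beginning retraction, for example "Closing retraction T-loops will be fabricated using 0.017 x 0.025 TMA wire" in the frictionless group.

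The Outcomes section makes T0 the baseline: "All outcomes will be assessed as the difference between T0 at the start of retraction and T1 after complete space closure". The Blinding section says that operators cannot be blinded, and that the principal operator assigns patients and takes the impressions. The Sample size section raises 10 per group to 15 for dropout, with no rate or stage. The Statistical Analysis section names no analysis set and no handling of patients without T0.

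One inconsistency bears on this. The Implementation section also has the patient draw the envelope at the time of intervention, whereas timeline item 7 starts active intervention only after levelling. The two statements must be reconciled.

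**The concern.** Randomisation balances the arms at the moment of allocation. Here a whole treatment phase lies between that moment and the baseline record, and the treating operator knows the arm throughout it. Two things can then depend on the arm when they need not.

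The first is who reaches T0. A patient who leaves during levelling has been randomised but has no T0-to-T1 change on models or cephalograms, so drops out of the comparison. If such losses differ by arm and are related to outcome, the patients compared are no longer the groups that were randomised.

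The second is when T0 is taken. The plan gives no explicit rule for levelling being complete. The Interventions section also allows a wait before retraction after miniscrew swelling or pain, which can move T0. Anchorage loss, molar rotation, torque and vertical position are total changes from T0, so they are more directly exposed than a rate of closure. Pain has no T0 measurement and is not affected in this way.

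The documents give no reason for allocating early, and nothing they describe before T0 depends on the arm.

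**Working it through.** **Order of events, side by side**

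| Step | Timeline item | Depends on arm? |
|---|---|---|
| Allocation | 5 | – |
| Miniscrews, extraction | 6 | No, given to every patient |
| Levelling and alignment | before active intervention (7) | No, one wire sequence for all |
| T0 model and cephalogram | 8 | No, but after allocation |
| Retraction | 9 | Yes, first difference |

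**The plan's own figure.** Inputs from the Sample size section: difference 1.0, SD 0.76, power 0.80, alpha 0.05 (taken as two-sided). n per group = 2 × [0.76 × (1.960 + 0.842) / 1.0]² = 9.07, rounded up to 10, as stated. Exact t-test power is 0.795 at 10 per group and 0.935 at 15. The rise to 15 allows for (15 − 10)/15 = 33% loss, which must cover loss both before and after T0.

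**Size of a selective loss before T0.** The documents give no levelling loss rate, so these inputs are assumptions. One arm loses a net excess of k = 1, 2 or 5 of 15 patients (5 is the plan's whole allowance). The other arm stays at 15. The lost patients' outcomes would have differed from those of the retained patients by d = 0.5 or 1.0 SD. There is no true difference between arms.

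- Shift in the between-arm difference, in SD units = (k/15) × d.
- Standard error in SD units = √[1/(15 − k) + 1/15].
- False-positive rate: two-sided 5% independent two-sample t-test, df = 28 − k, from the noncentral t with noncentrality shift/SE.

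| k | d | Shift (SD) | SE (SD) | False-positive rate |
|---|---|---|---|---|
| 1 | 0.5 | 0.033 | 0.372 | 5.1% |
| 1 | 1.0 | 0.067 | 0.372 | 5.3% |
| 2 | 0.5 | 0.067 | 0.379 | 5.3% |
| 2 | 1.0 | 0.133 | 0.379 | 6.3% |
| 5 | 0.5 | 0.167 | 0.408 | 6.8% |
| 5 | 1.0 | 0.333 | 0.408 | 12.3% |

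Multiplied by the SD of 0.76, the shift runs from 0.03 (0.033 × 0.76) to 0.25 (0.333 × 0.76), against a planned difference of 1.0. The Sample size section attaches no unit or named outcome to these figures, so the shift cannot be tied to a particular outcome. It is zero if loss is unrelated to outcome, or is equal in number and kind by arm.

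**Effect of T0 timing.** The documents contain nothing from which to estimate it. No figure is given.

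**Enrolment if allocation follows T0.** With assumed levelling losses of 0%, 10% and 20%, 30 enrolled gives 30, 27 or 24 randomised. To randomise 30, enrol 30/(1 − loss), rounded up: 30, 34 or 38.

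**The case against.** Both arms have the same written care until retraction, and nothing in the documents suggests unequal loss. For 1 or 2 patients the effect is small. The 12.3% figure needs the whole dropout allowance used up before T0, in one arm, by patients who all differ by 1 SD. The fixed wire sequence ends in the wire on which friction retraction starts, which limits discretion over when levelling is complete. Assessors are to be blinded, with names sealed on the records. And early allocation is not invalid in itself. All of this stands, and it keeps the point at the level of a cheap improvement.

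It does not dispose of the point. Sealed names protect the reading of records, not who reaches T0 or when it is taken. The Data collection section also has the principal investigator assess the secondary outcomes on models and films. That has to be reconciled with the Blinding section as a separate matter.

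A reader might infer that the operator also takes the T0 cephalogram knowing the arm. The documents do not support that. The film is obtained by referral, and nothing says that radiology staff know the arm. Only the general wording of timeline item 8 gives the principal investigator charge of the T0 records. What holds for the film is that it is obtained after allocation.

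It is also fair to say that the missing analysis set matters for losses after T0 too, and that re-timing does not cure those. Finally, re-timing may not be free: the Interventions section does not say when the T-loops are made.

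**Conclusion.** The point holds as an avoidable risk of bias that a small change removes. Allocation precedes a phase common to both arms, T0 follows allocation, the operator taking the T0 impression knows the arm, and no rule covers a patient lost before T0.

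A reader might infer that the trial's results are biased, or that its randomisation has failed. Neither follows. The size rests wholly on assumed losses: false-positive rates of 5.1% to 6.3% for a net excess of 1 or 2 patients, and 12.3% only at the extreme. The risk is zero if loss and T0 timing are unrelated to arm or to outcome. Nor is the matter mainly one of power, which is 0.935 with 15 completers per arm and 0.795 at the plan's 10. The change is worth making because early allocation has no stated benefit and, with allocation after T0, neither pre-T0 loss nor T0 timing can depend on the arm.

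**What to change.** Replace the Implementation sentence with: *Assignment will occur after levelling and alignment is complete and the T0 dental model and lateral cephalogram have been taken, before retraction begins.* Move timeline item 5 to after item 8, and bring the statement about when the envelope is drawn into line. Report patients lost before T0 as enrolled but not randomised. State whether enrolment stops at 30 or continues until 30 are randomised.

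For patients already allocated, report losses by arm, before and after T0, with reasons. Add to the Statistical Analysis section that the main estimate uses all randomised patients with T0 and follow-up data, in the arm assigned, with a sensitivity analysis for those without. Its assumptions should be fixed in advance. Filling in single fixed values would understate the standard error unless this is allowed for.

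Cost: one existing step moves later, with wording changes. If enrolment stays at 30, fewer than 30 may be randomised, but the number analysed is unchanged, because a patient lost in levelling has no T0-to-T1 outcome under either order. Keeping 30 randomised means enrolling and levelling more patients (34 at an assumed 10% loss, 38 at 20%), which matters in a self-funded project. T-loop preparation must fit between allocation and the start of retraction, which may need scheduling.

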Blinding of the operators: Blinding will not be possible for the operators during the application interventions and during the follow up visits. The principal operator is responsible for assigning subjects to interventions according to the concealed allocation, appliance activation at follow up visits, dental impressions and acquisition of dental casts.

Blinding of the outcome assessors: It is a single blinded study, therefore, only the outcome assessors will be blind. The patients name will be sealed from pre and post radiographs and study models. Then two assessors will carry out, blindly and independently, the measurements and analysis of the study.

III) Data collection, management and analysis:

A] Data collection methods:

Primary outcome:

1. Retraction rate: to assess the antero-posterior movement of anterior teeth and first molars, the principle investigator will take study models for every participant monthly during the follow up visits. Then, The models will be digitalized and the landmarks, reference lines and planes will be identified on the pre, interim and post-retraction digital dental models for measurements reading.

Secondary outcomes

1. Anchorage loss: will be accessed by the principal investigator via digitalized dental models taken before and after the completion of retraction by identifying the landmarks, reference lines and planes, then will interpret the measurements in millimeters.

2. Molar Rotation: will be accessed by the principal investigator via digitalized dental models. These records will be taken before and after the completion of retraction by identifying the landmarks, reference lines and planes, then will interpret the measurements of the angles in degrees.

3. Pain: Each patient will fill a questionnaire regarding his treatment experience in a VAS scoring from 1-10. The questionnaire will include several questions related to oral hygiene, pain and discomfort experienced throughout the trial.

4. Anterior teeth torque, extrusion/intrusion: will be accessed by the principle investigator via lateral cephalometric radiographs taken before and after the completion of retraction. The principal investigator will identify the landmarks, reference lines and planes, then will interpret the measurements in degrees and millimeters.

B] Data management:

A colleague outside the research team will enter the data and organize it in excel sheets in the computer of the orthodontic department.

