Data will include all photographs, models, radiographs and filled questionnaire.

C] Statistical Analysis:

- The principle investigator will be responsible for the extraction of the required data from the CBCT taken before and after retraction as well as the study models taken at every follow up visit. The data will be sent to a specialized statistician.
- The specialized statistician will be responsible for the statistical analysis of the study by:

1. Presenting the data as mean, standard deviation (SD) and Standard error (SE) values.
2. Using Paired t-test to compare between the friction and the frictionless group of retraction as well as to compare between the pre-and post -treatment data for each group.
3. Using Anova test to determine the rate of anterior segment retraction.

4. Statistically evaluate the patient acceptance for both techniques.

- For this study, the specialized statistician will use IBM11 SPSS12 Statistics Version 20 for Windows to perform the required statistics.
- The significance level will be $P \leq 0.05$. Highly significant variables are detected when P value is less than 0.01.

Assessors Reliability:

- To achieve high reliability for measurements, the supervisor will choose a well-experienced inter-examiner during the study.
- A training session will be provided for the examiners to ensure standard measurements techniques.
- Each examiner will complete the measurements on a model and will repeat the procedure after one week to assess the intra- and inter-examiner reliability.
- The supervisor will compare the measurements of the two assessors for disagreement with a difference of more than one millimeter.
- the supervisor will evaluate the amount of variation in measurements among and between examiners to test the performance of each assessor.
- The examiner with less reliability will receive additional training but will be replaced during the study.
- The specialized statistician will calibrate the intra and inter-examiner reliability for the measurements of the study by the Intra-class correlation coefficient (ICC). The closer the ICC to 1.0, the higher reliability between assessors. According to Fleiss: "ICC values between 0.7 and 0.9 represent good reliability." The kappa scores between study examiners will be calculated, a range of 0.60-0.80 will represent acceptable reliability.

IV) Method Monitoring:

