The main investigator will store any personal information about the participants collected during the study separately from study records in locked files in areas with only access to the supervisors responsible for auditing and analysis. Also, will keep the files in the Department Of Orthodontics, Faculty of Oral and Dental Medicine, Future University and will identify all the reports, data and administrative forms by a coded ID number to maintain participant confidentiality. Participant information won't be used outside the study except with written permission of the participant.

E] Declaration of interests:

No financial interests are to be declared by the supervisors and the principle operator. This study is a part of a Masters' degree in Orthodontics, Faculty of Oral and Dental Medicine, Future University and it is self-funded by the principal investigator.

F] Access to data:

The supervisors and the principal investigator will only have access to the data of the study. All the data will be secured by a password to maintain confidentiality. No other parties are allowed to assess the results until the study is terminated and the conclusions are revealed.

G] Ancillary and post-trial care:

Any complication associated with the intervention will be managed by the principal operator. Then the two group of patients will continue their regular orthodontic treatment according to the treatment plan described for each case.

H] Dissemination Policy:

The trial results will be available to the participants, health care professionals and the public by publication of the study in high quality national and international journals. The principal investigator will present a copy of the thesis at the Faculty of Oral and Dental Medicine, Future University library and will distribute additional copies among the main universities in Egypt.

References:

2. Meeran NA. Iatrogenic possibilities of orthodontic treatment and modalities of prevention. 2013;2(3):73-86. doi:10.4103/2278-0203.119678

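### Blinding is limited to the outcome assessors, yet the unblinded investigator is named to measure four secondary outcomes and extract the data, so the blind is not secured through to the result

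*Combined protocol and SAP*

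**What the plan says.** On who is blind, II) D] Blinding states: "It is a single blinded study, therefore, only the outcome assessors will be blind". Of the operators it says: "Blinding will not be possible for the operators during the application interventions and during the follow up visits". The assessors' blind rests on hiding identity: "The patients name will be sealed from pre and post radiographs and study models". The section continues: "Then two assessors will carry out, blindly and independently, the measurements and analysis of the study".

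On who measures, III) A] Data collection methods says otherwise: "Anchorage loss: will be accessed by the principal investigator via digitalized dental models taken before and after the completion of retraction". Molar rotation is given to the investigator in the same way. For torque and extrusion/intrusion the investigator identifies the landmarks and interprets the readings. For the retraction rate, the primary outcome, the investigator takes the monthly models, but the text does not say who reads them.

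On handling, III) B] Data management has a colleague outside the team enter the data. III) C] Statistical Analysis makes the principal investigator responsible for extracting data from the radiographic records and from the models of every follow-up visit, then adds: "The data will be sent to a specialized statistician". No sender is named and no masking of arms is mentioned. V) F] Access to data says: "The supervisors and the principal investigator will only have access to the data of the study". It sets no date before which the investigator is kept out.

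On knowledge of the arms, item 5 of the Participant timeline has the principal investigator allocate the patients. II) A] Sequence generation decodes the only labels in use: "to randomly assign patients to group A (Frictionless) or B (friction").

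**The concern.** Neither operator nor patient is blinded, so masked reading, handling and analysis are the only protection left against expectation affecting the result. Landmark placement on a digital model or cephalogram involves judgement. If the person placing landmarks knows the arm, differences of fractions of a millimetre or a few degrees can lean one way without any intent.

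Read as written, the plan allows this. One section promises blind, independent measurement by two assessors, while two others give measurement or extraction to someone who knows the allocation. Staff could follow either instruction and claim to have followed the protocol.

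After the reading, nothing describes a masked route to the statistician. The analysis list is also unsettled: it names a paired test for two independent groups, an ANOVA with no stated factors for the rate, and no test for patient acceptance. An analyst who can see the arms then has choices to make after seeing the data.

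**Working it through.** **1. Sections side by side.**

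- *Anchorage loss, molar rotation, torque, vertical position.* II) D]: two blinded assessors. III) A]: the principal investigator. These contradict each other.
- *Rate of space closure (primary).* II) D]: two blinded assessors, through the general statement. III) A]: reader not named. III) C]: the investigator extracts data from the models of every visit, which are the records that carry this outcome. Not settled.
- *Analysis.* II) D]: the two assessors. III) C]: the statistician. These contradict each other, and masking is described only for the assessors.
- *Data path.* III) B]: outside colleague enters. III) C]: investigator extracts. V) F]: supervisors and investigator have access. No route from blind reading to locked file is laid down.

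**2. Does the investigator know the arms?** Yes, from item 5 of the Participant timeline alone. That the investigator is also the treating operator is probable: the investigator takes the T0 and T1 records and continues treatment after the study, and the Declaration of interests describes a self-funded Master's project. It is not stated outright, and the point does not need it.

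**3. The plan's own figure.** Inputs from the sample size section: difference 1.0, SD 0.76, alpha 0.05 (two-sided assumed), power 0.8.

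n per group = 2 × [0.76 × (1.960 + 0.842) / 1.0]² = 9.07, rounded up to 10.

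The stated 10 per group is reproduced (t-based power at 10 is 0.795). The plan then enrols 15 per group. Nothing in this point changes the sample size.

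**4. Scale of a reading bias.** The documents give no figure, so the shift is an assumption. Suppose unblinded reading moves one arm by *s* when there is no true difference. The independent t-test then has noncentrality (s / 0.76) × √(15/2) at 15 per group:

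- s = 0.1: 0.36, false-positive rate about 6%
- s = 0.25: 0.90, about 14%
- s = 0.5: 1.80, about 41%

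Simulation with 40,000 trials agrees: 6.3%, 13.8% and 41.1%. The SD is the one assumed for the sample size. The secondary outcomes, some of them in degrees, will have other SDs, so read these shifts as fractions of an SD (0.13, 0.33, 0.66).

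**5. Scale of the open test choice.** III) C] names a paired t-test between arms, and the design calls for an independent one. Simulating both under no difference, with arbitrary pairing, the two statistics correlate 0.98 to 0.99. Taking the smaller p-value rejects in about 6.3% of trials at 15 per group and 6.4% to 6.6% at 10 per group, against a nominal 5%. With two arms, a one-way ANOVA is the same test as the independent t-test and adds nothing.

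**The case against.** The most charitable reading is that the intent is clear and only the wording is loose. The reliability section has two examiners repeat measurements and a supervisor compare them, so the plan plainly expects assessors to measure. The verb used for the investigator in III) A] may be a slip for obtaining the records. This reading fails on the text, because for torque and vertical position the investigator is said to place the landmarks and interpret the readings.

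Several stronger readings are tempting and should not be drawn:

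- *That the statistician knows the arms.* This is inferred from the word limiting the blind to the assessors, and from silence. The randomization codes are held at the secretary's office and records carry coded IDs, though for confidentiality. What can be said is that masking is not described.
- *That the investigator relays the assessors' readings.* III) C] describes extraction from source records and names no sender.
- *That the blind is undone after reading.* A reading made blind stays blind. The exposure is unblinded reading, and selective handling afterwards.
- *That masking would cure the test-choice inflation.* It would not. A two-sided p-value is the same whichever arm is called X. That inflation is also small, because the two t statistics are almost perfectly correlated.

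It is also fair to say that withholding readings hides little about progress from a treating operator, who sees the spaces closing every four weeks. The case for restricted access therefore rests on protecting the readings, not on keeping the operator ignorant of progress.

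**Conclusion.** The point holds in this form: blinding covers the assessors only and is not secured through to the result. Four secondary outcomes are assigned to an unblinded measurer, against the plan's own statement. The primary outcome has no named reader, extraction is given to the same unblinded person, the investigator's access has no restriction before lock, and masking of the statistician is not described. This goes beyond missing detail, since following III) A] and III) C] as written brings unblinded reading and handling into the results.

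The size of any bias is unknown. The figure of about 14% rests on an assumed shift of 0.25 with SD 0.76 at 15 per group. The figure of about 6.3% measures the unsettled test choice, assumes normal data and arbitrary pairing, and is a pre-specification matter separate from masking. The point should be put right before any results are seen. It does not invalidate the trial.

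**What to change.** Amend the following together, so that no section still contradicts another:

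1. **II) D] and III) A].** Make the two blinded assessors the sole readers of all model and cephalometric outcomes, including the rate of space closure. Replace the principal investigator as measurer in III) A].
2. **III) C], extraction.** Remove extraction from the investigator's duties. The assessors' readings go by coded ID directly to the data-entry colleague named in III) B].
3. **Access.** Give the investigator no access to the readings until all T1 records are read and the file is locked, and align V) F] with this.
4. **Arm code.** Have the secretary's office, which already holds the codes, supply a neutral X/Y code in place of A/B, which the protocol decodes. The statistician completes the analyses before the code is broken. Remove the assessors' role in analysis from II) D].
5. **Primary test.** Because masking does not prevent a choice between two-sided tests, name one independent-groups comparison of the rate as the primary test before the code is opened.

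No extra patients, visits or new roles are needed, since the assessors, the data-entry colleague and the secretary's office are already in the plan. The real cost is that measuring now assigned to the investigator passes to the assessors, which matters in a self-funded Master's project, and that the investigator cannot see results early.
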